Aim 3 will determine immediate and prolonged psychological reactions to biomarker disclosure among participants with MCI and DAT and their respective co-participants (e.g., care partners). We will assess changes in psychological status (both positive and negative) at two time points following disclosure relative to baseline. While one could predict changes in either direction, the above noted paucity of data in this area undermine the validity of such predictions. Thus, this aim is more descriptive in nature and provides critical information about cognitively symptomatic participants’ response to biomarker disclosure that will guide future research and translational efforts.

Aim 4 examines the impact of biomarker disclosure on co-participants as it relates to caregiving readiness and self-efficacy. We will assess changes in perceived readiness to provide care (to the participant) and caregiving self-efficacy at two time points following disclosure relative to baseline among co-participants who are either currently providing care to participants with MCI/DAT or who will hypothetically take on the caregiving role should the need arise. We predict that caregiving preparedness will be associated with the participant’s disclosed amyloid/tau result; specifically, an ‘elevated’ biomarker result is hypothesized to be associated with greater caregiving preparedness. Conversely, it is hypothesized that co-participants will have lower perceived readiness for caregiving if the participant’s amyloid/tau result is ‘not elevated.’

SECTION 2.3: Trial Design

The Education portion of the study is considered a Phase I/II Behavioral Intervention clinical trial without randomization. The Disclosure portion of the study is considered a Phase I/II Behavioral Intervention clinical trial without randomization, with the disclosure feedback serving as the intervention. The study will use a single-group design. All 100 participants (and any co-participants attending the first session) will complete the educational presentation and undergo an assessment of comprehension and decisional capacity. Those participants or dyads who meet criteria and demonstrate intact decisional capacity will be offered feedback about the participant’s PET amyloid and tau results. Outcomes will be measured immediately following feedback, within one week of disclosure, and at six-weeks post-disclosure. For more information regarding design, see *Methods* section.

SECTION 3: METHODS

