3.4 OUTCOMES

In addition to measuring **preliminary interest in PET disclosure after STIM activities (Aim 1, Primary Outcome 1)** and **Disclosure Decision-Making Capacity (overall and by component; Aim 2, Primary Outcome 2)**, we will collect the following outcome measures post-disclosure for participants who complete this step (Aim 3). These measures will be completed over the phone or via virtual visit to allow for maximum flexibility. Of note, we will also administer the GDS-15 and BAI at each time point for the purpose of safety monitoring (see DSMP); these are not considered primary outcomes. A summary of the outcome measure respondents and timeline is provided in Table 4.

Primary Outcome 3.1 - Comprehension & Recall: The Personal Information and Meaning of Information accuracy scores will be totaled for all participants and co-participants. Mean, median, and standard deviation will be calculated. Exploratory analyses will evaluate trends in whether specific types of feedback information (e.g., neuroimaging vs. amyloid/tau burden) were better understood than others, and whether group differences exist (i.e., participants vs. co-participants, by race, by cognitive status).

Primary Outcome 3.2 - Positive and Negative Affective Scale – Short Form (PANAS-SF¹⁸): This 20-item scale asks respondents to rate the extent to which they are experiencing positive (e.g., excited, inspired) and negative (e.g., distressed, ashamed) emotions on a Likert-style scale ranging from '1 = Very Slightly or Not at All' to '5=Extremely.' The two subscale scores range from 10-50, with higher scores indicating higher positive or negative emotions, respectively. The PANAS has demonstrated strong psychometric properties for assessing emotions in older adults¹⁹. This measure will be administered to both participants and co-participants.

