Primary Outcome 4.1 - Preparedness for Caregiving Scale (PCS^{29,30}): This 8-item measure assesses the degree to which care partners of persons with cognitive impairment (e.g., MCI, DAT) perceive they are prepared for and able to manage various domains of caregiving such as providing physical care and emotional support, setting up in-home support services, and coping with stress due to caregiving. Items use a 5-point likert scale ranging from 0 = 'Not at all prepared' to 4 'Very well prepared'. The PCS has demonstrated strong psychometric properties for assessing perceived readiness for caregiving among family members of persons with Alzheimer's disease dementia. This measure will be administered to study partners only.

Primary Outcome 4.2 - Revised Scale for Caregiving Self-Efficacy (RSSE³¹): The Revised Scale for Caregiving Self-Efficacy is a 15-item scale consisting of 3 sub-scales, each containing 5-items, designed to measure perceived ability to manage aspects related to caregiving among caregivers of persons with dementia. A single subscale consisting of 5-items will be used to measure co-participant's perceived ability to manage the emotional stresses associated with caregiving. This measure will be administered to study partners only.

Table 4. Outcome Measure Summary

Construct/Measure	Group (Participant, Study Partner, or Both)	Pre- Disclosure (Education Session)	Data Collection		Timepoint	
			Immediate Post- Disclosure	1-week	6-weeks	
Positive and Negative Affective Scale – Short Form	Both	X	X	X	X	
Impact of Neuroimaging in Alzheimer's Disease	Both		X	X	X	
Future Time Perspective Scale	Both	X	X	X	X	
Stigma Scale for Chronic Illness	Participant	X	X	X	X	
Self-Efficacy for Managing Chronic Disease Scale	Participant	X	X	X	X	
Revised Scale for Caregiving Self-Efficacy	Study Partner	X		X	X	

Preparedness for Caregiving	Study Partner	X		X	X
-----------------------------	---------------	---	--	---	---

SECTION 3.5 DATA MANAGEMENT & ANALYSIS

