3.5.2 Statistical Design

Data Screening

Prior to statistical analyses, data screening will be conducted. Initial steps will include a missing data analysis to determine randomness of missing data and range checks to assess for data quality. Additional screening for univariate and multivariate outliers, skewness and kurtosis will be conducted to inform needs for data transformation and statistical approach.

Statistical Approach

To assess Aim 1, we will compare the proportion of individuals in each diagnostic group who request vs. completed disclosure using a chi-squared test. Similarly, we will test hypotheses associated with Aim 2 (*greater disclosure decisional capacity in MCI than DAT*) by comparing the proportion of individuals in the DAT and MCI groups who demonstrate 'pass' scores on the DDMAT using a chi-squared test. We will also explore which particular elements of decision-making capacity may be more impaired in each group by comparing proportion of each diagnostic group who can adequately demonstrate understanding, appreciation, rationale, and communication on the DMAT using the same statistical strategy. To evaluate Aim 3, (*psychological reactions based on biomarker status*) we will compare participants' and co-participants' responses on outcome measures, based on amyloid and/or tau positivity vs. biomarker negativity. As we expect outcome measures to be correlated, we will utilize a 2 (diagnosis: MCI vs. DAT) by 2 (biomarker status: positive vs. negative) repeated measures analysis of variance (rmANOVA) approach for each follow-up time point. We will also compare differences in psychological reactions between participants and co-participants by diagnosis (MCI vs. DAT) using a paired t-test on all continuous items and a chi-squared test on categorical items. To evaluate Aim 4 (*impact of biomarker disclosure on co-participant caregiving readiness and self-efficacy*), we will similarly compare co-participants' responses, based on amyloid and/or tau positivity vs. biomarker negativity. As we expect outcome measures to be correlated, we will utilize a 2 (participant's diagnosis: MCI vs. DAT) by 2 (biomarker status: positive vs. negative) repeated measures analysis of variance (rmANOVA) approach for each follow-up time point.

SECTION 4: MONITORING

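### Ten outcomes are labelled primary, and seven of them go to significance tests at two or three visits with no stated alpha, lead visit or error control, although Aim 3 is declared descriptive and Aim 4's prediction names no visit

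*Combined protocol and SAP*

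**What the plan says.** Section 3.4 attaches the word primary to ten outcomes:

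- Outcome 1, "preliminary interest in PET disclosure after STIM activities (Aim 1, Primary Outcome 1".
- Outcome 2, "Disclosure Decision-Making Capacity (overall and by component; Aim 2, Primary Outcome 2".
- Outcomes 3.1 to 3.6: comprehension and recall, PANAS-SF, INI-AD, SSCI-8, the chronic-disease self-efficacy scale (SECD) and Future Time Perspective (FTP).
- Outcome 4.1, the Preparedness for Caregiving Scale (PCS), and "Primary Outcome 4.2 - Revised Scale for Caregiving Self-Efficacy" (RSSE), of which one subscale is used.

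The Primary Outcomes row of the summary table at the front of the document lists eight and omits both caregiver scales.

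Section 3.5.2 handles these outcomes in different ways. Outcomes 1 and 2 get chi-squared comparisons between MCI and DAT. For Aim 3 it plans a 2 (diagnosis) by 2 (biomarker status) "repeated measures analysis of variance (rmANOVA) approach for each follow-up time point", and also compares participants with co-participants "using a paired t-test on all continuous items". For Aim 4, "we will similarly compare co-participants' responses, based on amyloid and/or tau positivity vs. biomarker negativity", with the same 2 by 2 analysis at each follow-up. Outcome 3.1 is summarised in Section 3.4: "Mean, median, and standard deviation will be calculated", with group differences labelled exploratory.

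Section 2.2 says of Aim 3: "Thus, this aim is more descriptive in nature". For Aim 4 it predicts greater caregiving preparedness after an elevated result and lower readiness after a non-elevated one. It names no visit.

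**The concern.** Two parts of the plan disagree about what Aim 3 is for. Section 2.2 disclaims any prediction, while Section 3.4 makes its outcomes primary and Section 3.5.2 sends 3.2 to 3.6 to significance tests. With no lead outcome or visit and no error control, a chance difference on one scale at one visit could be reported as a primary result about learning of an elevated scan.

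Aim 4 does carry a directional prediction, but a reader cannot tell which visit decides it. Nor does the plan say whether a self-efficacy result would count as support. Section 2.2 expects the results to guide later research and translation, so it matters whether a reported difference was the planned test or the most favourable of many.

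**Working it through.** **No figure to reproduce.** The documents give no alpha, power, effect size or error rate. Two-sided 0.05 is my assumption throughout.

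**Inputs (Section 3.4 and Table 4).** PANAS-SF, INI-AD and FTP go to both respondent groups, SSCI-8 and SECD to participants only, and PCS and RSSE to study partners only. The first five are collected at three post-disclosure visits and the last two at two. Section 3.4 gives PANAS-SF two subscale scores. The INI-AD covers positive and distressing reactions, and Section 4.1.1 refers to its distress subscale, so I count two scores for each.

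**Reading A: each score tested separately, biomarker effect only.**

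- Participants: (2 + 2 + 1 + 1 + 1) = 7 scores × 3 visits = 21.
- Co-participants: (2 + 2 + 1) = 5 scores × 3 visits = 15.
- Aim 4: 2 scores × 2 visits = 4.
- Total: 21 + 15 + 4 = 40.

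Under no effect, the expected number of false positives is 40 × 0.05 = 2.0. If the tests are independent, the chance of at least one is 1 − (1 − 0.05)^k:

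- k = 40: 1 − 0.95^40 = 0.871.

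For correlated tests I used a one-factor normal model, Z_i = √ρ·F + √(1 − ρ)·e_i, and the chance that any |Z_i| exceeds 1.96:

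- ρ = 0.5: 0.571.
- ρ = 0.7: 0.375.

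**Sensitivity to the count and correlation model.** One score per scale, plus one test each for Aims 1 and 2, gives 15 + 9 + 4 + 2 = 30 tests. The two-score count plus the same two tests gives 42. The correlated column assumes 0.3 to 0.6 between scales and 0.5 to 0.8 between visits, with the respondent groups and the Aim 4 block independent of each other.

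| Tests | Independent | Correlated |
|---|---|---|
| 30 | 78.5% | 57% to 72% |
| 42 | 88.4% | 65% to 82% |

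**Reading B: scales pooled within a visit.** There is one model per respondent group per visit: 3 + 3 + 2 = 8 biomarker main effects. 1 − 0.95^8 = 0.337 if independent, and lower if correlated.

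**Aim 4 alone.** The correlated ends of the two-sided ranges use a between-visit correlation of up to 0.8 for the PCS pair and a uniform correlation of up to 0.7 for the four tests.

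| What counts as support | Tests | Independent, two-sided | Range, two-sided | Predicted direction only |
|---|---|---|---|---|
| PCS at 1 or 6 weeks | 2 | 1 − 0.95² = 9.75% | 8% to 10% | 4% to 5% |
| PCS or self-efficacy, either visit | 4 | 1 − 0.95⁴ = 18.5% | 13% to 19% | 7% to 10% |

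The prediction in Section 2.2 is worded for preparedness and readiness, so the first row is the one it supports.

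**The case against.** The strongest reply is that the plan is better ordered than the label suggests. Section 3.5.2 ties Aim 2's hypothesis to one identifiable test, the overall DDMAT pass proportion in MCI against DAT, and describes the component comparisons as exploration. Outcomes 1 and 2 have no biomarker factor and no repeated visits, and 3.1 is already summarised descriptively. Aim 3 is declared descriptive, and the trial is a non-randomised, single-group Phase I/II supplement. All of this stands. It limits the point to seven outcomes and leaves Aim 2 as it is.

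The rmANOVA wording is also open. Because it is justified by correlated outcome measures, it may mean that scales are pooled within a visit, which gives about 8 models and not 40. That reading is tenable, so both figures belong in the record. In the other direction, diagnosis and interaction effects, the paired comparisons and the undefined amyloid and/or tau grouping could all raise the count.

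A reader might infer more than the documents support:

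- *That a chance finding is near certain.* The range under Reading A is about 38% to 87%, and the plan itself expects correlated measures.
- *That the plan tests at 5%.* No alpha is stated anywhere, which is part of the gap.
- *That most scales are tested in both respondent groups.* Three of the seven in Table 4 are.
- *That Aim 4's prediction can be claimed from any of four tests.* Self-efficacy is within the aim's scope but not in its written prediction, so two tests apply.

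The early-phase argument does not remove the conflict. An aim described as descriptive should not have primary outcomes that are tested for significance with no rule for reading the results.

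**Conclusion.** The point holds in limited form. The primary label on 3.2 to 3.6, together with their planned significance tests, conflicts with Section 2.2, and Aim 4 has no named visit for its prediction. If scores are tested separately, a false positive somewhere is likely but not near certain; the estimate falls below even only at the uniform correlation of 0.7. If scales are pooled, it is about 34% at most under these assumptions. For Aim 4 as written the inflation is modest: 8% to 10% two-sided, or 4% to 5% in the predicted direction. It rises to 13% to 19% two-sided only if self-efficacy also counts as support. All figures rest on an assumed two-sided 0.05, no true effects and assumed correlations. The conflict between the two sections does not depend on any of them.

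**What to change.** 1. State the alpha and whether tests are one- or two-sided.
2. Keep overall DDMAT pass, MCI against DAT, as the single confirmatory test for Aim 2.
3. For Aim 4, name PCS by disclosed result at one pre-specified visit as the single confirmatory test. Six weeks would serve as an example; the documents favour neither visit. Make the other PCS visit and the self-efficacy subscale secondary, in a stated fixed order or with Holm. One named test returns the Aim 4 error to 5%. If all four tests are to stay equal in status, Bonferroni at 0.05/4 = 0.0125 each gives 1 − 0.9875⁴ = 4.9% under independence.
4. Relabel 3.2 to 3.6 as descriptive, with 3.1, and report them as estimates with 95% intervals and no significance claims, in line with Section 2.2.
5. State whether the rmANOVA is fitted per scale or pools scales within a visit.
6. Make the Primary Outcomes row of the summary table match Section 3.4.

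The cost is wording in Sections 3.4 and 3.5.2 and in the summary table. No visit, measure or participant changes. The downside is fewer formal significance claims, chiefly for Aim 3.

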4.1 Risk Monitoring

4.1.1 Part I: Education & Decision-Making Assessment

Participants who endorse current/active depression, anxiety, or other significant psychological disorder will be excluded from the study. Prior to other study activities but after informed consent has been provided, participants will be screened using the Geriatric Depression Scale – 15 Item version (GDS-15)¹ and the Beck Anxiety Inventory (BAI)² to ensure no active depressive/anxiety symptoms. Each of the measures have empirically supported cut-off scores (GDS-15 \geq 9; BAI \geq 16) for determining clinically significant depression, anxiety, and event-related distress; individuals who endorse clinically significant depression or anxiety on the GDS-15 or BAI will be withdrawn from the study prior to further participation. These measures will be repeated at each of the three follow-up time points (immediate, within 1 week, 6 weeks) to assess change in mood or anxiety symptoms; those with elevations at or above the cutoffs noted above will complete an additional assessment with a clinically licensed team member to determine next steps, adverse events, and resources. Additionally, participants complete the INI-AD at the immediate, one-week, and six-week follow-up sessions. Any participants scoring 24 or higher on the distress subscale of the INI-AD will complete a follow-up assessment by a clinically licensed study team member.

It is not expected that discussing AD, DAT, and PET disclosure will cause significant distress or exacerbation of mood symptoms; however, any participant who appears distressed during the session will undergo risk assessment and intervention as needed according to the study safety plan (Appendix A). Of note, for video or phone sessions, at the start of each session, the participant/co-participant will be asked to provide a call-back number in case he/she is disconnected from the technology, as well as current location; this information will not be stored after study completion in the participant's/co-participant's file, but will be used as a reference in case of emergency or safety issue.

Unanticipated adverse events or serious adverse events deemed related to study participation (i.e., acute exacerbation or onset of severe depression or anxiety, hospitalization for emotional reasons, and/or preparation for or engagement in self-injurious behavior as a result of risk disclosure results) will be reported immediately to the study PI. Consistent with Office of Human Research Protection, Institutional Review Board guidelines for the study's parent institution, and NIA standards, serious study-related adverse events resulting in life-threatening outcome or death will be reported to the SO and NIA program officer as soon as possible, and within 24 hours of study PI knowledge of the event. Other serious study-related adverse events and unanticipated adverse events will be reported as soon as possible, and within 48 hours of study PI knowledge of the event. The PI, in conjunction with the SO, will review the case and relevant study data to determine whether the study should be halted or how it may be altered to promote safety.

Additionally, the SO will meet at least twice per year via telephone or video conferencing to review adverse events and their outcomes, and to generate recommendations for study protocol alteration for improved safety (or termination of the study, if deemed necessary).

SECTION 5: ETHICS AND DISSEMINATION

5.1 Research Ethics Approval & Protocol Amendments

All procedures detailed above fall within the parameters approved by the University of Michigan institutional review board. Any changes to these parameters or procedures will be proposed to and approved by the IRB through formal amendments prior to implementation.

5.2 Consent or Assent

All consent forms and others requiring authorized signatures will be approved by the University of Michigan IRB. There are separate consent forms for Part I: Education & Decision-Making Assessment and Part II: Disclosure. A study team member will review the appropriate consent form with the participant and their LAR/DPOA as applicable. The team member will pause after each section to solicit and answer questions. Comprehension of the procedures, risks, benefits, and other aspects of the study will be checked using the Consent Decision-Making Assessment Tool (CDMAT), a brief measure asking the participant to use their own words to review the contents of each section of the consent form before signing. If the participant no longer retains the ability to provide informed consent, the designated LAR/DPOA will be asked to provide consent, and the participant will be asked to provide assent. Alternatively, if the participant no longer retains the ability to provide consent but brings a co-participant who is not a designated LAR/DPOA, the participant may allow that individual to provide consent, and the participant will be asked to provide assent.

As detailed above, these procedures will be completed virtually prior to the first visit to ensure sufficient time to answer all questions. The participant will then print, sign, scan, and return the consent form or utilize the SignNow modality to electronically sign the document and return it to the study team member, who will sign it.

The study team member will then download the completed form, and store electronically under password protection in the network secure drive. As mentioned above, a copy of the consent form is uploaded into the participant's University of Michigan electronic medical record as a 'Research Document' to communicate current research participation to medical providers.

5.3 Confidentiality

Information gathered from individuals contacted for initial screening is entered into a recruitment database file that is stored in the shared drive (accessible only to approved lab personnel) and password protected. This centralized file will contain only the necessary information for contacting and determining eligibility and interest in the study, as well as assigned ID numbers for enrolled participants and any co-participants. For information regarding security and confidentiality of data from enrolled participants/co-participants, see '**Data Management & Entry**'.

Participants will be made aware prior to enrollment in Part I that they will not receive feedback regarding their PET amyloid and tau status during this stage of the study. This option will not be offered to participants until completion of and evaluation of responses from Part I.

